#### 4.2 Secondary Efficacy Endpoints

- Mean number of COVID-19 symptoms (range 0 – 13) at day 3, 7, 10 and 14 of the patient symptoms' diary. This endpoint will be derived using the Covid-19 Symptoms Form of the eCRF at

DAY 3, DAY 7, DAY 10 and DAY 14. For each subject, the number of symptoms reported as 'Yes' will be calculated, adding one if the symptom "Fever" is greater than 38°.

- Duration of COVID-19 symptoms, defined as the number of days between randomization and complete disappearance of symptoms. More specifically, duration of COVID-19 symptoms will be taken as day of complete disappearance (because randomization is DAY 0). Subjects who will still have at least one symptom at their last assessment will be censored at the day of this last assessment.

To determine day of complete disappearance of symptoms, all symptom assessments from the patient's diary will be sorted by day (variable DAYPARM). At each time point, the assessment will be categorized as complete disappearance of symptoms (if number of symptoms = 0) or no complete disappearance of symptoms (if number of symptoms > 0).

- ✓ If there is complete disappearance of symptoms at Day 14 (or last assessment), day of complete disappearance is the first day when complete disappearance occurred with no relapse.
- ✓ If there is no complete disappearance of symptoms at Day 14 (or last assessment), the day of this last assessment will be the censoring day.

It should also be noted that subjects who do not complete the study will be classified as still having symptoms (i.e. no complete disappearance) REGARDLESS if symptoms disappeared earlier. Date of censoring will be the date of study discontinuation.

- For each of the 13 COVID-19 symptoms listed in the appendix, proportion of subjects with the symptom at day 3, 7, 10 and 14 of the patient symptoms' diary. Presence of these symptoms (Yes/No) will be identified using the Covid-19 Symptoms Form of the eCRF (variables COUGH, FEVER [considered a symptom if greater than 38°], FEVERISH, STHROAT, ..., ANOS) at DAY 3, DAY 7, DAY 10 and DAY 14.

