#### 6.2.1 Handling of Missing Data

Subjects will be asked to assess daily the presence (Yes/No) of 13 COVID-19 symptoms for a duration of 14 days. Most efficacy endpoints rely heavily on the assessment of these symptoms so a rule has to be defined in case the symptoms are reported as 'Not Done' or are missing.

At any given day (DAY 1 to DAY 14), if some symptoms among the 13 symptoms are reported as 'Not Done' or are missing, these symptoms will be imputed as the last observation carried forward.

On the other hand, if, at any given day, all symptoms are reported as 'Not Done' or are missing, the following will be done:

- If the subject has died, then all symptoms will be imputed as 'Yes' (and symptom "Fever" as greater than 38°) if that day is prior to date of death.

- Otherwise, the symptoms will not be imputed and the assessment on that day will be considered missing.

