#### 6.4.2 Secondary Analysis

- Number of COVID-19 symptoms (range 0 – 13) will be summarized using descriptive statistics at 3, 7, 10 and 14 days, overall and by treatment group.

Mean number of COVID-19 symptoms will be compared between treatment groups using a repeated measures analysis of variance (ANOVA) model with terms for treatment group (placebo, hesperidin), time (3, 7, 10 and 14 days) and treatment group x time interaction. Contrasts under this model will allow for the comparisons of the mean number of symptoms at each time point. Mean differences will be presented with 95% confidence intervals and p-values. If more appropriate given the distribution of the data, a Poisson regression model for repeated measures could be used.

- Number and proportion of subjects with complete disappearance of COVID-19 symptoms after randomization will be provided overall and by treatment group. In those subjects, duration of symptoms will be summarized using descriptive statistics.

Duration of COVID-19 symptoms will be compared between treatment groups using a log rank test and Kaplan-Meier curves will be presented.

- Individual COVID-19 symptoms over time (3, 7, 10 and 14 days) will be presented and analyzed as the primary endpoint, using the statistical approach described in section 6.4.1.

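### The symptom-duration analysis has no rule for death: a patient who dies is censored as though still able to recover, which overstates cumulative recovery in that arm

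*SAP*

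**What the plan says.** SAP 4.2 has symptom duration "defined as the number of days between randomization and complete disappearance of symptoms". Two rules in that section deal with subjects who do not reach the event:

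- Subjects symptomatic at the end: "If there is no complete disappearance of symptoms at Day 14 (or last assessment), the day of this last assessment will be the censoring day".
- Non-completers: "subjects who do not complete the study will be classified as still having symptoms (i.e. no complete disappearance) REGARDLESS if symptoms disappeared earlier", followed by "Date of censoring will be the date of study discontinuation".

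Neither rule names death. SAP 6.4.2 gives the method, "Duration of COVID-19 symptoms will be compared between treatment groups using a log rank test", with Kaplan-Meier curves and no competing-risk method. Protocol 8.3.1 is also silent on death for this endpoint.

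Death is considered elsewhere. SAP 6.2.1 has an imputation rule for days on which every symptom is missing: "If the subject has died, then all symptoms will be imputed as" present, but only "if that day is prior to date of death". SAP 4.3 includes death in the exploratory composite, and SAP 6.5.2.2 provides a listing of deaths.

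**The concern.** Kaplan-Meier and log-rank methods take a censored patient out of the risk set and assume that, had follow-up continued, the patient would have had the event at the rate of those who remain. That is reasonable for someone who stops answering the telephone. It is not reasonable for someone who has died, who cannot go on to recover.

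One minus the Kaplan-Meier estimate at Day 14 is then no longer the share of the arm that recovered. Each death is in effect replaced by an average surviving patient, so an arm with deaths is not charged for them. If the treatment did harm, part of that harm would be missing from the duration comparison.

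**Working it through.** **Which rule reaches a death.** A patient who dies before Day 14 cannot complete the study, so the non-completer rule in SAP 4.2 applies. That the discontinuation date equals the date of death is an inference. The conclusion does not depend on it: the other rule censors at the last assessment, which cannot fall after death, and nothing in 4.2 carries the patient on to Day 14.

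**The plan's own figures.** None is given for duration or deaths. The sample size in SAP 6.1 reproduces with the unpooled formula: (1.96 + 0.8416)² × (0.25 + 0.21) / 0.20² = 90.26, so 91 per group; 91 / 0.85 = 107.06, so 108 per group. It serves here only to turn percentages into patients: one death in 108 is 0.93%.

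**Inputs.** Follow-up of 14 days is from the SAP. The rest are assumptions: a fraction d of the arm dies while symptomatic, spread evenly over Days 4-9; the others recover with a constant daily hazard h = 1 − (1 − R)^(1/14), where R is 14-day recovery, taken as 50% to 80%. There is no other drop-out.

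**Case 1: deaths strike symptomatic patients at random.** Under the SAP rule Kaplan-Meier returns R, as if no one had died. A death on Day k removes a patient who would have recovered by Day 14 with probability 1 − (1 − R)^((14 − k)/14), so

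overstatement = d × mean over k = 4…9 of [1 − (1 − R)^((14 − k)/14)].

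- R = 50%: (0.390 + 0.360 + 0.327 + 0.293 + 0.257 + 0.219) / 6 = 0.308
- R = 80%: (0.683 + 0.645 + 0.601 + 0.553 + 0.498 + 0.437) / 6 = 0.570

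That is 0.31 to 0.57 points for each 1% who die. Two deaths in 108 (1.85%) give 1.85 × 0.308 = 0.57 to 1.85 × 0.570 = 1.05 points.

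**Case 2: those who die would never have recovered, and the rest recover at R.** True cumulative recovery is (1 − d)R. Kaplan-Meier under the SAP rule is 1 − Π[1 − h·s/(s + m)] over Days 1-14, where s = (1 − d)(1 − h)^(day − 1) and m is the number destined to die who are still at risk (d up to Day 4, then falling by d/6 after each of Days 4-9).

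| Deaths | R | KM, SAP rule | True recovery | Overstatement | KM in a death-free arm |
|---|---|---|---|---|---|
| 1% | 50% | 49.81% | 49.50% | 0.31 | 50% |
| 1% | 80% | 79.77% | 79.20% | 0.57 | 80% |
| 2% | 50% | 49.61% | 49.00% | 0.61 | 50% |
| 2% | 80% | 79.54% | 78.40% | 1.14 | 80% |
| 4% | 50% | 49.22% | 48.00% | 1.22 | 50% |
| 4% | 80% | 79.06% | 76.80% | 2.26 | 80% |

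The overstatement is nearly the same in both cases, but the arm with deaths ends level with a death-free arm (Case 1) or slightly below it (Case 2).

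**Case 3: both arms have the same underlying recovery, and deaths in one arm fall only on patients who would not have recovered by Day 14 anyway.** Simulation with 108 per arm, deaths on Days 5-14, 14-day recovery of 30-70%, 1,000 runs per setting. Compared with keeping the deceased at risk to Day 14:

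| Deaths in one arm | Rise in Day-14 recovery (points) | Log-rank Z shift towards that arm |
|---|---|---|
| 1 | 0.1-0.3 | 0.01-0.03 |
| 2 | 0.2-0.5 | 0.03-0.06 |
| 5 | 0.5-1.4 | 0.07-0.16 |
| 10 | 1.0-3.3 | 0.15-0.35 |

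Here the arm with deaths does gain. With ten deaths, a false result in its favour occurs in 3.3% to 6.0% of runs against a nominal 2.5% (Monte Carlo error about 0.5-0.8 points). When the same simulation placed deaths at random among symptomatic patients, mean Z stayed between about −0.04 and +0.06.

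**The case against.** Censoring at death is a recognised analysis. The log-rank test then compares the rate of recovery among patients who are alive and symptomatic, which is a legitimate question. Keeping the deceased in the risk set to Day 14 answers a different one. This stands to the extent that the change is a choice of estimand and must be declared. It does not rescue the Kaplan-Meier curve, whose Day-14 value would be read as the share who recovered.

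Deaths are also visible elsewhere: in the composite, in the safety tables and death listing, to the DSMB, and in the crude proportion with complete disappearance in SAP 6.4.2, where a patient who dies counts as unresolved. That stands, so harm would not be hidden from the trial as a whole.

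The effect is small. With 108 per arm and 50% recovery, the standard error of the difference between arms is √(2 × 0.25 / 108) = 6.8 points, against about 1 point or less for two deaths. That stands too.

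A reader might also infer that SAP 6.2.1 contradicts 4.2 by scoring death as all symptoms present. It does not. The imputation covers only fully missing days before the date of death, and later days are left missing. Read together, the two sections have the patient symptomatic until death and without data afterwards.

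**Conclusion.** The gap is real and minor. SAP 4.2 by default censors a patient who dies as though recovery were still possible. With deaths on Days 4-9 and 50-80% recovery in the others, Day-14 recovery in that arm is overstated by about 0.3 to 0.6 points per 1% of the arm that dies. Later deaths or slower recovery make it smaller. The documents give no death rate, recovery rate or timing of deaths, so the size depends on these assumptions. Few deaths are likely in outpatients followed for 14 days.

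A reader might go further and infer that the arm with more deaths will look better than the other arm. The documents do not support that. The arm looks better than it should, which is a weaker statement. In general the deaths are ignored or only partly counted; an actual advantage arises only if those who die would have recovered slowly or not at all while the other arm keeps comparable patients under follow-up, as in Case 3.

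**What to change.** Add to SAP 4.2, before unblinding, that a subject who dies before Day 14 is analysed as not recovered and is censored at Day 14. The deceased then stay in the risk set for both the curve and the log-rank test. A cumulative incidence curve with death as a competing event, compared by Gray's test, would serve the same purpose.

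State beside it that the curve shows cumulative recovery with death counted as no recovery, and not the rate of recovery among those still alive. For clarity, SAP 6.2.1 could say outright that days on or after death are left missing.

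The cost is one sentence and one line of code. The downside is small: the estimand changes and must be declared. If the blind has already been broken, report this as a sensitivity analysis beside the planned one.

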#### 4.3 Tertiary (or Exploratory) Efficacy Endpoints

- For each of the 13 COVID-19 symptoms listed in the appendix, proportion of subjects with the symptom on a daily basis based on patient's diary. Presence of these symptoms (Yes/No) will be identified using the Covid-19 Symptoms Form of the eCRF (variables COUGH, FEVER [considered a symptom if greater than 38°], FEVERISH, STHROAT, ..., ANOS) at DAY 1 to DAY 14.
- Composite of COVID-19-related hospitalization, mechanic ventilation or death in the 14 days following randomization. These events will be identified using the Adverse Events Form of the CRF:
  - ✓ COVID-19 related hospitalization: AECOVID=YES and AESER=YES and AESHOSP=YES; date of hospitalization = ADMDAT
  - ✓ COVID-19 related mechanic ventilation: AECOVID=YES and AEVENT=YES; date of mechanic ventilation = AEVSDTA
  - ✓ COVID-19 death: AECOVID=YES and AEOUT=Fatal; date of death = AEENDAT1

## 5 SAFETY PARAMETERS

Safety will be assessed through adverse events (AEs) and serious adverse events (SAEs).

### 5.1 Adverse Events

Information regarding AEs will be collected at day 3, 7, 10 and 14 after randomization. Any AEs prior to randomization will be recorded in the medical history and kept in the patients' chart. Information collected will include the onset, end date (if applicable), severity, relationship to study drug, and the management.

A treatment-emergent AE is an AE which started on or after the date of the first dose of study medication. In case the date of first dose of study medication is unknown, the AE will be assumed to be treatment-emergent if it started on or after the study medication delivery date.

In case the day the AE started is unknown (month and year are required fields for the AE start date), the AE will be assumed to be treatment-emergent if it started on the same month and year as the date of first dose of study medication (or study medication delivery date); otherwise the partial AE start date will be compared to the date of first dose of study medication (or study medication delivery date) and the AE will be classified accordingly.

A related AE is one where, according to the investigator, there is a reasonable possibility that the event may have been caused by the study drug. They will be identified from the Adverse Events Form of the eCRF as AEs that are possibly or probably related to study drug.

### 5.2 Serious Adverse Events

Serious Adverse Events (SAE) are those that meet any of the following International Council for Harmonisation (ICH) criteria:

- Is fatal or immediately life-threatening (NOTE: the term "Life-Threatening" refers to an event in which the patient was at immediate risk of death at the time of the event; it does not refer to an event which could hypothetically have caused death had it been more severe);
- Results in persistent or significant disability/incapacity;
- Requires or prolongs patient hospitalization;
- Is a congenital anomaly/birth defect in the offspring of the patient;
- Is a cancer;
- Is an overdose (intentional or accidental);
- Is judged to be medically important.

Medically important events may not be immediately life-threatening, result in death or hospitalization, but may jeopardize the patient or may require intervention to prevent one of the outcomes listed in the definition above. Serious adverse events are to be reported if they are known to occur within 21 days after randomization.

## 6 STATISTICAL METHODOLOGY

### 6.1 Determination of Sample Size

Sample size is based on the proportion of subjects with any of the following COVID-19 symptoms: fever, cough, shortness of breath or anosmia at day 7 since this time point will be the primary focus. Using a two-sided 0.05 significance level, sample sizes of 91 in both groups (182 total) will achieve 80% power to detect an absolute between groups difference of 20% in the proportion of subjects with the above COVID-19 symptoms at day 7. This is assuming that the proportions of patients with the above COVID-19 symptoms at day 7 will be 50% in the placebo group and 30% in the active treatment group. Factoring in a 15% drop out rate, a total of 216 patients will be randomized in the study (108 per group).

### 6.2 Statistical Considerations

Baseline, efficacy and safety data will be reported using descriptive statistics. N, mean, standard deviation, median, Q1, Q3, minimum and maximum will be provided for continuous variables. Count and frequency will be provided for categorical variables.

Basic assumptions of the proposed analyses will be verified prior to the analyses. Subject disposition, datasets analyzed, baseline characteristics and efficacy analyses will be carried out on the ITT population defined in Section 3.1 according to the intent to treat principle. Safety analyses will be done on the safety population defined in Section 3.2.

All statistical tests will be two-sided and conducted at the 0.05 significance level. Statistical analyses will be done using SAS version 9.4 or higher.

A fully independent 3-member Data and Safety Monitoring Board (DSMB) will be established and will review unblinded data as detailed in the DSMB charter after randomization of 50, 100 and possibly 150 subjects. The DSMB charter will pre-specify the rules for early study termination, approved by all board members.

#### 6.2.1 Handling of Missing Data

Subjects will be asked to assess daily the presence (Yes/No) of 13 COVID-19 symptoms for a duration of 14 days. Most efficacy endpoints rely heavily on the assessment of these symptoms so a rule has to be defined in case the symptoms are reported as 'Not Done' or are missing.

At any given day (DAY 1 to DAY 14), if some symptoms among the 13 symptoms are reported as 'Not Done' or are missing, these symptoms will be imputed as the last observation carried forward.

On the other hand, if, at any given day, all symptoms are reported as 'Not Done' or are missing, the following will be done:

- If the subject has died, then all symptoms will be imputed as 'Yes' (and symptom "Fever" as greater than 38°) if that day is prior to date of death.

- Otherwise, the symptoms will not be imputed and the assessment on that day will be considered missing.

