### 4 EFFICACY ENDPOINTS

#### 4.1 Primary Efficacy Endpoint

The primary endpoint will be the proportion of subjects with any of the following COVID-19 symptoms: fever, cough, shortness of breath or anosmia, at day 3, 7, 10 and 14 of the patient's symptoms diary.

Presence of these symptoms (Yes/No) will be identified using the Covid-19 Symptoms Form of the eCRF (variables COUGH, FEVER [considered a symptom if greater than 38°], SBREATH and ANOS respectively) at DAY 3, DAY 7, DAY 10 and DAY 14.

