## 8 APPENDICES

### APPENDIX A COVID-19\_ SYMPTOMS LOG

Symptoms	Day 1 Yes No	Day 2 Yes No	Day 3 Yes No	Day 4 Yes No	Day 5 Yes No	Day 6 Yes No	Day 7 Yes No
Recent cough or aggravation of chronic cough	 						
Fever (enter temperature)							
Feverish/chills (temperature not taken)	 						
Sore throat	 						
Runny nose	 						
Shortness of breath/difficulty breathing	 						
Nausea/vomiting	 						
Headache	 						
General weakness	 						
Pain (muscular, chest, abdominal, joint, etc.)	 						
Irritability/confusion	 						
Diarrhea	 						
Sudden Loss of smell (anosmia)	 						
Comment or other, specify:							

Reminder: Please have the completed diary on hand at each phone call or video contact follow up.

Symptoms	Day 8 Yes No	Day 9 Yes No	Day 10 Yes No	Day 11 Yes No	Day 12 Yes No	Day 13 Yes No	Day 14 Yes No
Recent cough or aggravation of chronic cough	 						
Fever (enter temperature)							
Feverish/chills (temperature not taken)	 						
Sore throat	 						
Runny nose	 						
Shortness of breath/difficulty breathing	 						
Nausea/vomiting	 						
Headache	 						
General weakness	 						
Pain (muscular, chest, abdominal, joint, etc.)	 						
Irritability/confusion	 						
Diarrhea	 						
Sudden Loss of smell (anosmia)	 						
Comment or other, specify:							

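### SAP 6.2.1 carries an old Feverish/chills answer across days with a recorded temperature, which can delay or censor recovery in the secondary endpoints

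*SAP*

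**What the plan says.** **Missing items.** SAP 6.2.1 states: "Subjects will be asked to assess daily the presence (Yes/No) of 13 COVID-19 symptoms" over 14 days. When only part of a day's log is absent, the previous value is brought forward: "if some symptoms among the 13 symptoms are reported as 'Not Done' or are missing, these symptoms will be imputed as the last observation". There is no limit on how long a value may be carried. The only other branch covers days on which all 13 items are absent: positive if the patient died later, otherwise missing.

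**The log.** SAP Appendix A (the same log as Protocol Appendix E) has two linked rows. One is "Fever (enter temperature"), with space for a reading and no Yes/No boxes. The other is "Feverish/chills (temperature not taken"), with Yes/No boxes every day.

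**Endpoints.** In SAP 4.1 the primary composite uses cough, shortness of breath, anosmia and "FEVER [considered a symptom if greater than 38" degrees]. Feverish/chills is not part of it. In SAP 4.2, "the number of symptoms reported as 'Yes' will be calculated", with one more for a temperature above 38, so the two rows are separate items in the 0 to 13 range. Recovery needs "complete disappearance of symptoms (if number of symptoms = 0"), and "day of complete disappearance is the first day when complete disappearance occurred with no relapse". A patient above zero at the last assessment is censored there.

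No sentence in SAP 4.1 to 4.3, SAP 6.2.1 or the diary instructions says how the two fever rows relate.

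**The concern.** For most rows a blank is an unanswered question. For Feverish/chills, a blank on a day with a recorded temperature can also mean that the row did not apply. SAP 6.2.1 treats both as missing and imports the previous answer. A patient who ticked Yes on Day 1, before taking a temperature, and then recorded normal temperatures while skipping the row would count as feverish through Day 14. One carried item is enough to keep the count above zero, and recovery requires zero.

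The reverse gap is smaller. On a day without a temperature, FEVER has no value, so the last reading is carried even when the patient answered Feverish/chills that day. The old reading may be above or below 38, so the error can go either way. This reaches the primary composite, but only if cough, shortness of breath and anosmia are all absent on that day.

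**Working it through.** **1. The plan's sample size (SAP 6.1).** Inputs: 50% vs 30% at Day 7, two-sided 0.05, 80% power, 15% dropout. The unpooled formula gives n = (1.960 + 0.842)² × (0.5×0.5 + 0.3×0.7) / 0.20² = 7.849 × 0.46 / 0.04 = 90.26, so 91 per group. Then 91 / 0.85 = 107.06, so 108 per group and 216 in total. The stated figures reproduce and are not in dispute.

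**2. Trace for Feverish/chills.** One non-composite symptom is present on Days 1–5 and absent afterwards. Feverish/chills is Yes without a temperature on Day 1. On Days 2–14 the temperature is 37.0 and the Feverish/chills row is blank.

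| | Count, Day 1 | Days 2–5 | Days 6–14 | Duration |
|---|---|---|---|---|
| SAP rule | 2 | 2 | 1 | censored, Day 14 |
| Unanswered row derived as No when a temperature exists | 2 | 1 | 0 | recovered, Day 6 |

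The primary composite is negative on Day 7 under both. If both fever rows are blank on Day 14, the results do not change, provided later carry-forward starts from the derived No.

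**3. One explicit No.** A single No on Day 3, 7, 10 or 14 moves the SAP result from censored to recovery on Day 6, 7, 10 or 14; the derived rule gives Day 6 each time. So a later No removes the censoring, but recovery cannot be dated before it. If No is entered daily from Day 2, both rules give Day 6.

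**4. Trace for a missing temperature, all other items No.**
- Readings of 38.5 on Days 1–4, then no temperature and Feverish/chills No on Days 5–14: FEVER stays positive, the Day 7 composite is positive, and duration is censored at Day 14.
- Readings of 37.0 on Days 1–4, then no temperature and Feverish/chills Yes on Days 5–8: FEVER stays negative and the Day 7 composite is negative.

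**5. Size for duration.** Let f be the share of patients in each arm censored as in step 2. The documents give no f, no hazard ratio, no recovered share and no power target for this endpoint, so all are assumptions. The simulation used 92 per arm (216 × 0.85 / 2 = 91.8), hazard ratio 1.6, exponential recovery rounded up to whole days, cut-off at Day 14 and a two-sided 0.05 log-rank test, with 20,000 trials per scenario (Monte Carlo standard error about 0.3 points). With 60% recovered, the observed share is 60% × (1 − f), and events are 184 times that.

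| f | Patients of 184 | Events (60% recovered) | Power, 50% recovered | Power, 60% | Power, 70% |
|---|---|---|---|---|---|
| 0 | 0 | 110 | 60.8% | 69.9% | 76.1% |
| 1% | 2 | 109 | 60.2% | 68.2% | 74.3% |
| 2% | 4 | 108 | 60.1% | 67.4% | 73.7% |
| 5% | 9 | 105 | 57.4% | 64.0% | 69.4% |
| 10% | 18 | 99 | 52.7% | 58.8% | 63.2% |

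At hazard ratio 1 and 60% recovered, the type I error for f = 0/2/5/10% was 5.03/5.20/5.14/5.12%. The mean count on late days rises by about f.

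**6. Size for the primary endpoint.** If a share g of composite-free patients becomes positive on Day 7, p′ = p + g(1 − p). If a share h of composite-positive patients becomes negative, p′ = p(1 − h). In each case the difference shrinks to 0.20 × (1 − g) or 0.20 × (1 − h). Power = Φ{[|p₁ − p₂| − 1.96√(2p̄(1 − p̄)/91)] / √[(p₁(1 − p₁) + p₂(1 − p₂))/91]}, the pooled form, which starts at 79.1% (80.3% unpooled).

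| Assumed share | Old high reading carried (g) | Power | Old normal reading carried (h) | Power |
|---|---|---|---|---|
| 0.5% | 50.25 vs 30.35% | 78.6% | 49.75 vs 29.85% | 78.8% |
| 1% | 50.5 vs 30.7% | 78.1% | 49.5 vs 29.7% | 78.4% |
| 2% | 51.0 vs 31.4% | 77.1% | 49.0 vs 29.4% | 77.7% |

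**The case against.** The endpoints come from the eCRF, not the paper log. Annotated CRF version 2.0, on which the SAP is based, is not in the documents. The log has only Yes/No boxes, while SAP 6.2.1 speaks of Not Done, so the coding differs somewhere. If staff enter No for every unused Feverish/chills row, the main problem disappears. The SAP expects all 13 items daily, and staff complete the form by phone on Days 3, 7, 10 and 14 with the diary at hand. Patients also receive a thermometer and must be able to use it daily, and one later reading of 38 or below ends a carried fever. All of this stands. It limits how often the patterns can occur, but no passage tells staff how to code the unused row, and a missing-data rule exists for such departures.

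A reader might infer that the rule overwrites recorded data. It does not: it fills a missing item. Nor does a normal temperature prove the absence of chills. The objection is only that a blank in a conditional row is weak evidence for repeating an old Yes.

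A reader might also infer that the primary derivation should change so that a Feverish/chills No sets fever to No. That would be one-sided: the second trace in step 4 would still carry an old normal reading over a same-day Yes. It would also let a self-report decide a component that SAP 4.1 defines by measured temperature.

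**Conclusion.** The point holds as a conditional one. SAP 6.2.1 as written gives an implausible result on a diary pattern that the log makes foreseeable, if unused Feverish/chills rows reach the eCRF as blank or Not Done. The main effect is on the symptom count, the Feverish/chills proportions and duration, which are secondary and exploratory endpoints. Under the assumptions above, with 60% recovered, the loss of log-rank power is about 2 points at f = 1 to 2% and 6 points at f = 5%. The primary endpoint loses at most about 2 points at an assumed 2%.

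The documents do not support a claim of a false-positive risk or of a materially biased primary result. Allocation is blinded, the simulated type I error stays near 5%, and equal misclassification in both arms dilutes the difference. The frequency is unknown, so the importance is minor. It is worth raising because the rule is explicit and the correction is short. The simulation leaves out the 15% dropouts, whereas SAP 4.2 keeps non-completers as censored; its figures are illustrative.

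**What to change.** Before unblinding, amend SAP 6.2.1 and its derivation code:

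1. When a temperature is recorded and Feverish/chills is blank or Not Done, do not carry Feverish/chills forward. Derive it as No for that day. Keep any same-day Yes, and let later carry-forward start from the derived value.
2. Leave the primary FEVER derivation (above 38) and the 0 to 13 range unchanged. Add a sensitivity analysis for days with no temperature but an answered Feverish/chills row, in which the fever component takes the same-day answer in both directions. On such days a Yes counts once in the symptom total, not twice.
3. Report by arm how many patient-days items 1 and 2 change, and state how CRF version 2.0 codes an unused Feverish/chills row.

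The cost is SAP wording and code; no new data are needed. Item 1 does not touch the primary endpoint. Its downside is that unreported chills on a day with a temperature count as absent. Because item 2 is only a sensitivity analysis, the patterns in step 4 remain in the main analysis, but their effect becomes visible. If CRF version 2.0 already codes unused rows as No, item 1 changes nothing.
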